#### Hypothesis Test

The NRS objective will be assessed by the following hypotheses:

$$\begin{split} H_0: \ \mu NRS_T \ - \ \mu NRS_C \geq 0 \\ H_A: \ \mu NRS_T \ - \ \mu NRS_C < 0, \end{split}$$

where  $\mu$ NRST is the mean change in NRS from baseline to 1 year in the Treatment group and  $\mu$ NRSC is the mean change in NRS from baseline to 1 year in the Control group. These hypotheses will be tested using 1-year contrast from an MMRM as described above.

#### 3.1.2.2. EQ-5D

The EQ-5D-5L (referred to as EQ-5D throughout this document) is a quality-of-life questionnaire comprising of the following 5 dimensions: mobility, self-care, usual activities, pain/discomfort and anxiety/depression.

Population norms for EQ-5D for various populations have been reported, and categorized by age, gender and social class. EQ-5D is reported as an index up to 1.00. An EQ-5D index score of <0 is possible in some circumstances.

The endpoint will compare change from baseline in EQ-5D between Treatment and Control groups at the 1-year visit.

#### Hypothesis Test

The EQ-5D efficacy objective will be tested under the following hypotheses:

 $\begin{array}{l} H_0: \ \mu EQ5D_T \ - \ \mu EQ5D_C \leq 0 \\ H_A: \ \mu EQ5D_T \ - \ \mu EQ5D_C > 0 \end{array}$ 

Where  $\mu EQ5D_T$  is the mean change in EQ-5D (index score) in the Treatment group and  $\mu EQ5D_C$  is the mean change in EQ-5D in the Control group. These hypotheses will be tested using 1-year contrast from an MMRM as described above.

#### 3.1.3. Tertiary Endpoints

#### 3.1.3.1. Percent Pain Relief (PPR)

Percent Pain Relief (PPR) is a question asked to the patient in which the patient is asked to report the percent pain relief at the time of the current visit compared to the pain at baseline.

The endpoint will compare PPR at the 1-year visit between Treatment and Control groups in descriptive analyses.

#### 3.1.3.2. Subject Global Impression of Change (SGIC)

Subject Global Impression of Change (SGIC) is based on the "Subject Global Impression of Change" as described by Farrar. The patient is presented with a questionnaire with 7 choices, as shown in Figure 5.

#### Figure 5: Subject Global Impression of Change (SGIC) Questionnaire

The endpoint will compare SGIC at the 1-year visit between Treatment and Control groups in descriptive analyses.

#### 3.1.3.3. Treatment Satisfaction

Treatment satisfaction will be measured by a single question as shown in Figure 6.

Are you satisfied with the outcome of your treatment?				
Definitely yes	□ Maybe	Definitely not		

#### Figure 6: Treatment Satisfaction Question

The endpoint will compare Treatment Satisfaction at the 1-year visit between Treatment and Control groups.

#### 3.1.3.4. ODI and NRS Composite

Patients suffering from CLBP are continuously balancing their activity level with their level of pain. As their condition improves, patients make personal choices on whether to increase their level of activity while tolerating a certain level of pain, or to continue with the same level of activity as earlier but with less discomfort, or somewhere in between. These choices are based on the

patients' individual circumstances and preferences. Therefore, when evaluating a therapy for CLBP, an evaluation of improvements in pain interpreted in conjunction with functional improvements allows for a more comprehensive assessment of the therapy.

This endpoint will compare the percent of patients with a change in  $ODI \ge 15$  or a reduction in NRS  $\ge 50\%$  (and no decrease in either measure) at the 1-year visit between Treatment and Control groups.

#### 3.1.3.5. Leg Pain NRS

Average Leg Pain will be measured using an 11-point Numerical Rating Scale for Leg Pain. The patient will rate his/her average leg pain in the last 24 hours on a scale from zero to ten, where zero is no pain and ten is the worst imaginable pain

The endpoint will compare change from baseline in Leg Pain NRS between Treatment and Control groups at the 1-year visit.

#### 3.1.4. Safety Assessment

Reportable adverse events (AEs) are those related to the device, procedure, stimulation or other therapies utilized to treat LBP, and all serious adverse events (SAEs), whether related or not.

All reportable AEs will be documented and reported from the time of informed consent through the end of the study with summary statistics presented for observed rates. No formal statistical hypotheses will be tested in the safety assessment. The following definitions are used:

#### Adverse Event (AE):

An AE is defined as any undesirable clinical occurrence that affects the health or safety of the patient.

#### Serious Adverse Event (SAE):

An SAE is defined as an AE that led to death, or led to serious deterioration in the health of the patient, that either resulted in:

- 1. a life-threatening illness or injury, or
- 2. a permanent impairment of a body structure or a body function, or
- 3. in-patient or prolonged hospitalization,
- 4. congenital anomaly/birth defect, or
- 5. medical or surgical intervention to prevent life-threatening illness or injury or permanent impairment to a body structure or a body function.

#### Unanticipated Adverse Device Effect (UADE):

A UADE means any serious adverse effect on health or safety or any life-threatening problem or death caused by or associated with a device, if that effect, problem, or death was not previously identified in nature, severity, or degree of incidence in the protocol or application, or any other unanticipated serious problem associated with a device that relates to the rights, safety, or welfare of patients.

#### Adverse Event Relatedness:

The Investigator must determine whether the event was related to the device, stimulation, procedure, and/or other therapies. The categories used for relatedness are listed in Table 2.

Related to Device	Events reasonably anticipated to be related to the physical presence of the device (e.g., lead fracture requiring revision).
Related to Stimulation	Events reasonably anticipated to be related to stimulation, especially those that appear when the device is on and disappear when the device is off (e.g., undesired sensation experienced only when the device is turned on).
Related to Procedure	Events reasonably anticipated to be related to the implant procedure.
Related to Other Therapies	Events reasonably anticipated to be related to treatments being utilized to treat the patient's LBP (e.g., medications, injections, physical therapy).

#### **Table 2: Adverse Event Relatedness Categories**

#### AE Notes:

- 1. AEs that would be reasonably expected to be associated with any surgical procedure and are not specific to the ReActiv8 procedure (e.g., anesthesia associated nausea, transient post-op surgical site pain) will not be collected.
- 2. If an AE leads to multiple outcomes that sequentially worsen, only the worst AE is reported. For example, a hematoma leading to infection is reported as a single AE for the infection.
- 3. Any current condition that is recorded as a pre-existing condition is not an AE, unless there is a worsening of that condition in terms of nature, severity, or degree of incidence.
- 4. Removing, suspending or stopping use of ReActiv8 due to pain relieved is not an AE.
- 5. Planned hospitalization for a procedure required by this protocol is not an AE.
- 6. Symptoms felt during a programming session are not considered AEs unless they are caused by the final programming parameters and persist after the programming session.
- 7. Lack of efficacy or diminished therapeutic response does not constitute an AE since failure to receive therapeutic benefit is an issue of efficacy, not safety. This includes symptoms that recur in the context of device deficiency leading to loss of therapy. If the recurring symptoms are not worse than at baseline, it is not considered an AE.
- 8. Removal or replacement of any part of the device due to malfunction would be considered a device related AE, since it requires the patient to undergo a surgical procedure.
- 9. Death should not be recorded as a separate AE, but rather as an outcome of the specific SAE which led to the patient's death.

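### AE Note 2 keeps only the worst event of a worsening chain, so earlier events that qualify in their own right drop out of the AE counts

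*Protocol*

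**What the plan says.** Protocol section 3.1.4 makes reportable any AE related to the device, procedure, stimulation or other back-pain therapy, "and all serious adverse events (SAEs), whether related or not". It then commits: "All reportable AEs will be documented and reported from the time of informed consent through the end of the study with summary statistics presented" as observed rates. SAP section 5.9 repeats this. Protocol section 7.1 adds that all related AEs, all SAEs and all UADEs go to investigators and IRBs.

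The AE Notes in the same section 3.1.4 narrow this. Note 2 reads: "If an AE leads to multiple outcomes that sequentially worsen, only the worst AE is reported". Its illustration is that "a hematoma leading to infection is reported as a single AE for the infection".

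Two neighbouring notes bear on the point. Note 8 treats removal or replacement of a device part for malfunction as a device-related AE. Note 9 records a death as the outcome of the SAE that caused it, not as a separate AE.

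Relatedness is assigned by the investigator under Table 2, and the wording above that table allows more than one category for an event. On inference, the plan says: "No formal statistical hypotheses will be tested in the safety assessment".

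**The concern.** With no safety hypothesis, the descriptive AE summary is the trial's whole safety result. A counting rule that leaves out qualifying events changes that result directly. A reader of the final tables could not tell how many infections began as hematomas, and the hematoma rate itself would be too low.

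The rule is also open at several points. It sets no severity scale for deciding which event is worst. It does not say what happens to a hematoma already entered on the AE form when the infection appears. Read literally, it would also leave out a precursor that was itself an SAE, if something worse followed.

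**Working it through.** The plan states no AE rate or count, so there is no figure to reproduce. The check is mainly textual.

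**1. Note 2 applied to its own example.** Two clinical events (hematoma, infection) become one reported AE. In general, a chain of k events is counted as 1, so k − 1 are not counted. The example has a point only if the hematoma would otherwise count as an AE.

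**2. Note 2 against the reporting commitments.**

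| Place | What is reported |
|---|---|
| Protocol 3.1.4, opening | All reportable AEs, including all SAEs |
| Protocol 7.1 | All related AEs, all SAEs, all UADEs |
| SAP 5.9 | Same scope as Protocol 3.1.4; no rule on chains |
| Protocol 3.1.4, Note 2 | Only the worst event of a worsening chain; no exception for a serious, UADE or device-related precursor |

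A procedure-related hematoma that becomes infected is reportable under the first three rows and not under the fourth.

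**3. Note 2 against Notes 8 and 9.** Nothing says which of Note 2 and Note 8 prevails when a replacement for malfunction leads to something worse. Note 9 works the other way round from Note 2: it keeps the causing event and treats the end of the chain as its outcome.

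**4. Relatedness.** No text makes the reported event inherit the precursor's relatedness or seriousness, and no text says that these are lost. Loss is possible, not prescribed.

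**5. Effect on summaries.** Each chain still yields one AE, so the number of patients with at least one AE is unchanged. Event counts, and patient counts by event type, can be lower.

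**6. Illustrative size (assumed rates).** About 230 patients randomized 1:1 gives 230 / 2 = 115 in the Treatment arm. Assume that 10% have a relevant AE: 0.10 × 115 = 11.5, about 12 patients. Assume that 10% to 30% of these progress to a second event: 12 × 0.10 = 1.2 and 12 × 0.30 = 3.6, so about 1 to 4 precursors go uncounted.

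As a share: if a fraction s of reported AEs each ends a chain of m events, the unreported share of all events is s(m − 1) / [1 + s(m − 1)].

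| s (assumed) | m = 2 | m = 3 |
|---|---|---|
| 5% | 0.05/1.05 = 4.8% | 0.10/1.10 = 9.1% |
| 10% | 0.10/1.10 = 9.1% | 0.20/1.20 = 16.7% |
| 20% | 0.20/1.20 = 16.7% | 0.40/1.40 = 28.6% |

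**7. Which arm.** Under Protocol Table 3 only the Treatment group is implanted before the 1-year visit, so implant-related chains in the randomized year arise there. Note 2 formally covers both arms, including chains that start from medication or injections.

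**The case against.** The best defence is that Note 2 is a disclosed counting convention. It sits in the same section as the reporting commitment, so the two can be read as a general rule and its refinement. It prevents duplicate entries for one evolving complication, and it keeps each chain at its worst severity. No safety test depends on it.

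Other routes also keep some of the information. Sites file records of any related AE or SAE (Protocol 7.6). Device deficiencies go to Complaint Handling (7.2). Related AEs and SAEs are collected at revision or explant (5.12). Note 8 protects replacements for malfunction.

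Part of this stands. Avoiding duplicates is a proper aim, and precursors are not lost from every record. But site files and complaint records are not the study AE dataset, a hematoma is not a device deficiency, and Note 8 reaches only removal or replacement for malfunction. The refinement reading also leaves Protocol 7.1 and the SAE and UADE commitments without a stated exception.

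A reader might go further and infer that device failures disappear from the device-related count, for example when a lead fracture leads to revision and then to a wound infection. The documents do not support that as a stated effect. Such an infection is not clearly a worsening of the fracture, Note 8 may preserve the device event, and the infection may be coded to both device and procedure.

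**Conclusion.** The point holds as a reporting gap and an inconsistency. Followed as written, Note 2 takes independently reportable precursors out of the AE counts, against Protocol 3.1.4 (opening), Protocol 7.1 and SAP 5.9, and its relation to Note 8 is undefined. Relatedness may be lost as well, but need not be.

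The size cannot be derived from the documents. The 1 to 4 events rest wholly on the assumed 10% AE rate and 10-30% progression. The efficacy analyses are untouched.

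Two further inferences should be resisted. One is that onset dates shift to the later event: the documents give no onset-date rule. The other is that planned tables by event type or relatedness are biased: the plan promises only observed rates, so type-specific understatement arises in whatever breakdown is eventually produced.

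**What to change.** - **Protocol 3.1.4, Note 2:** replace it with a rule that each event in a chain that meets the reportable-AE definition by itself is recorded with its own onset, seriousness and relatedness, and linked to its precursor. Symptoms of a single diagnosis remain one AE.
- **Same note:** state that it does not override Note 8 or the reporting of SAEs and UADEs, so that it agrees with section 7.1.
- **SAP 5.9:** present both the number of patients with at least one event, which avoids double counting, and the number of events.

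The cost is a short protocol edit, a linking field on the AE form and one SAP line. The downside is slightly more AE entries and a somewhat higher event count. If enrollment is well advanced, the site records kept under Protocol 7.6 may allow earlier chains to be linked retrospectively.

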## 5.4. Activation (Treatment Group)

Data to be collected:

• Related AEs and all SAEs

Activities to be performed:

- Inspect surgical wound to verify healing and remove sutures (if not previously removed)
- Perform electrode impedance and threshold measurements and program the IPG
- Device download
- Train in use of the Activator and document assessment of patient's ability to selfadminister therapy twice a day starting the next day
- Train in the procedure to deliver stimulation, including time of day and positioning
- Download activity monitoring data (if applicable)

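### AE Note 6, read literally, excludes symptoms that outlast a programming session if a discarded setting caused them, and in year 1 it can lower AE counts only in the ReActiv8 arm

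*Protocol*

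**What the plan says.** Note 6, among the AE Notes of Protocol Section 3.1.4, says that symptoms felt in a programming session "are not considered AEs unless they are caused by the final programming parameters and persist after the programming session".

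The surrounding definitions are wider:

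- **General definition:** "An AE is defined as any undesirable clinical occurrence that affects the health or safety of the patient".
- **Reportable events:** "Reportable adverse events (AEs) are those related to the device, procedure, stimulation or other therapies utilized to treat LBP", together with all SAEs. SAP Section 5.9 repeats this rule but does not carry the AE Notes.
- **Table 2, stimulation category:** "Events reasonably anticipated to be related to stimulation", with no restriction to settings that were kept.
- **SAE:** "An SAE is defined as an AE that led to death, or led to serious deterioration in the health of the patient", followed by a list of outcomes.
- **UADE:** "A UADE means any serious adverse effect on health or safety or any life-threatening problem or death caused by or associated with a device", provided that it was not previously identified in nature, severity or incidence. Protocol Section 7.1 lists UADEs for reporting separately from related AEs and SAEs.

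For the Treatment group, Section 5.4 has staff at Activation "Perform electrode impedance and threshold measurements and program the IPG". Sections 5.5 to 5.7 then allow the stimulation configuration to be adjusted where needed at 1.5, 3, 6 and 12 months. Section 1.1 lets Control patients be implanted in the study only after the 1-year visit. Protocol Section 3.1.4 and SAP Section 5.9 both make the safety assessment descriptive, without hypothesis tests.

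**The concern.** Excluding a passing sensation that stops with the session is sensible, and the persistence condition does that unaided. The added condition on final parameters can remove only symptoms that do persist. A programming session may include stimulation at settings that are tried and not retained, so a symptom can arise from a setting that is no longer in use when the session ends.

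Safety in this trial rests entirely on descriptive rates, so the counting rule determines what is reported. A rule that can act in only one randomised arm can shift the year-1 comparison in only one direction. Notes 3 and 7, which also exclude events, leave genuine worsening reportable. Note 6 has no such clause and no exception for serious outcomes.

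**Working it through.** The plan states no figure for this rule. Its one computed figure, 204 evaluable patients, concerns ODI and does not enter here. The check is mainly a comparison of texts.

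**1. What Note 6 does.** A symptom felt in a session falls into one of four cases:

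| Setting responsible | Persists after session | AE under Note 6 | AE if persistence alone decided |
|---|---|---|---|
| Final | Yes | Yes | Yes |
| Final | No | No | No |
| Discarded | No | No | No |
| Discarded | Yes | **No** | **Yes** |

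The final-parameters condition changes one case only, the lasting symptom from a discarded setting.

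**2. Against the general definitions.** A lasting symptom of that kind can be an undesirable occurrence affecting health and can be related to stimulation. Without Note 6 it would be an AE in the stimulation category, and hence reportable. With Note 6 it is not.

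**3. Serious events.** The SAE definition starts from an AE, so an occurrence ruled out as an AE cannot, on the wording, become an SAE. The UADE definition does not start from an AE, so a serious unanticipated effect is still captured. What remains uncovered is a serious effect that was already identified, was felt as a symptom in the session and came from a setting not kept.

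**4. Which arm.** Through the 1-year visit the Treatment group has up to five scheduled programming contacts: Activation, then 1.5, 3, 6 and 12 months. Control has none under the protocol. SAP Section 5.8 foresees Control patients leaving to obtain the device commercially, but they are withdrawn from the study. Implanted Controls come under Note 6 only after 1 year.

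**5. Exposure.** About 230 patients randomised 1:1 gives 230 / 2 = 115 in Treatment. The ceiling on scheduled contacts in year 1 is 115 × 5 = 575. It is a ceiling because adjustment after Activation happens only where needed, and because it assumes that every patient is implanted and retained. Activation alone gives at most 115.

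**6. Illustrative size.** The documents give no rate. Assume that a share q of Treatment patients has at least one such symptom in year 1, independently between patients. The expected number of patients is 115 × q, and the chance of at least one is 1 − (1 − q)^115.

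| Assumed q | Expected uncounted patients | Chance of at least one |
|---|---|---|
| 0 | 0 | 0% |
| 0.1% | 0.1 | 11% |
| 0.5% | 0.6 | 44% |
| 1% | 1.2 | 69% |
| 2% | 2.3 | 90% |
| 5% | 5.8 | 99.7% |

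With 102 Treatment patients (204 / 2) the expected numbers fall by the factor 102 / 115 = 0.89. The corresponding number in Control is 0 throughout year 1.

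**The case against.** **The notes are part of the definitions.** Section 3.1.4 presents definitions and notes together, and several other notes also carve out events. On that view Note 6 is a specific qualification of a general rule, and SAP Section 5.9 sets no competing AE definition. This stands to the extent that the passages differ in breadth and are not in formal contradiction. It does not explain why a lasting symptom should be classified by the setting that caused it.

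**A reader might infer that lasting harm from test stimulation can never be recorded.** The documents do not support that. Note 6 is confined to symptoms felt in the session. Harm with later onset, and objective findings, fall outside it.

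**A reader might infer that serious harm has no reporting route.** That also goes too far, because the UADE route stays open for serious unanticipated effects.

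**A reader might infer that year-1 harm is in fact undercounted and that ReActiv8 will look safer than it is.** Nothing in the documents shows that such symptoms occur. Table 2 describes stimulation-related events as mostly those that stop when the device is off, which suggests that lasting ones may be rare. Only a possible undercount is established.

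**The consequence is limited.** The safety rates are descriptive, and the ODI test, its error rate and its power are untouched. That is correct, and it keeps the point a matter of wording. It does not remove it, because descriptive rates are all the safety evidence the plan will produce.

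**Conclusion.** The point holds in a narrow form. As worded, Note 6 excludes one identifiable class of event: a symptom felt in a programming session that lasts beyond it and was caused by a setting not retained. This is narrower than the general AE definition and Table 2. Through the SAE definition it also narrows SAE capture, apart from what the UADE route catches.

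During the randomised year any effect on counts falls on the ReActiv8 arm alone and can only lower them. Its size is unknown and may be zero. The assumed range of 0.1% to 5% of 115 patients gives about 0.1 to 5.8 patients, but that only illustrates scale and is not evidence of a rate. The conclusion rests on sites applying the note literally and on Controls having no programming under the protocol before the 1-year visit. It is an inexpensive improvement to a counting rule and does not challenge the efficacy analysis.

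**What to change.** Reconcile Note 6 with the AE and SAE definitions, Table 2, the reportable-event rule in Protocol Section 3.1.4 and SAP Section 5.9 by removing the final-parameters condition. Suggested sense: a symptom felt in a programming session is not an AE unless it continues after the session, whichever setting caused it, or results in any of the serious outcomes listed in the SAE definition. The exception should point to the list of outcomes. Pointing to the SAE definition as a whole would be circular, since that definition already requires an AE. Sensations that end with the session stay excluded unless they lead to a listed outcome.

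Apply the same rule to events already recorded where source data allow, and state in the report where they do not, so that counts under two rules are not mixed unnoticed.

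The cost is one protocol sentence and matching AE form instructions. Under Protocol Section 8.1 that means Sponsor and Investigator agreement, a recorded justification and local approval such as IRB submission. The device arm may show a few more stimulation-related AEs.
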